7.3 Study Population

Participants of PCOS with NAFLD will be recruited for this study.

Number of Participants Planned:

A total 90 participants (including 20% dropouts) was planned to enrolled across USA and Mexico in a ratio of 1:1 to have 45 participants in each treatment arm i.e., Saroglitazar Magnesium 4 mg and placebo.

Six participants in each group are planned for pharmacokinetic assessment therefore a total of 12 participants will be included for pharmacokinetic assessment.

In view of the difficulty and challenges observed in recruitment of study population, it is decided to close recruitment at 60 participants.

7.4 Randomization

An independent statistician will generate the randomization schedule(s) for study treatment assignment. Eligible participants will be randomized in a 1:1 ratio to receive Saroglitazar Magnesium 4 mg or placebo respectively. Block randomization will be performed. The block randomization schedule will be generated to ensure the treatment balance by using SAS® software (Version: 9.4 or higher; SAS Institute Inc., USA).

7.5 Blinding and Unblinding

The study will be performed in a double-blind manner. All study drug will be supplied in identical packages and study drug kits. The study drug tablets will be similar in color, smell, taste, and appearance, thereby maintaining double-blind conditions.

The study blind should not be broken except in a medical emergency where knowledge of the study drug received would affect the treatment of the emergency.

The blind must only be broken following a discussion on a case-by-case basis, at the discretion of the Sponsor/Medical Expert. If an emergency unblinding becomes necessary, the PI should notify the Sponsor/Medical Expert, if possible, before unblinding. If it is determined that unblinding is necessary, a scratch card will be decoded to reveal the treatment received by the participant. All cases resulting in an unblinding event will be documented and reported to the Medical Expert and the Sponsor. If the blind is

Document Title:	Statistical Analysis Plan		
Version Number:	Final 1.0	Date:	18Oct2024
Protocol Number:	SARO.17.009	Sponsor Name:	Zydus Therapeutics INC

broken, the date, time and reason must be recorded in the participant's eCRF/source document and any associated AE report completed.

The overall randomization code will be broken only for reporting purposes. This will occur once all final clinical data have been entered into the database, all data queries have been resolved, and the assignment of participants to the analysis sets has been completed.

Emergency code break (Unblinding):

An emergency code break will be available to the investigator and / or pharmacist. This code break must only be opened in emergency situations when the identity of the study drug must be known by the investigator in order to provide appropriate medical treatment. If the code break for a Participant is opened, Sponsor must be informed immediately. The reason for opening the code break must be documented along with the date and the initials of the person who broke the code. Participants whose treatment assignment becomes unblinded inadvertently, need not complete the scheduled evaluations and participant will be withdrawn from the trial from that visit.

7.6 Investigational Products

The Investigational products that will be used in this study are outlined in the following table:

Study drug	Formulation	Strength	Route	Manufacturer
Saroglitzaz Magnesium	Tablet	4 mg	Oral	[REDACTED]

Dosage and Treatment Schedule:

Participants will receive either 4 mg Saroglitzaz Magnesium or placebo orally once each morning before breakfast without food, for 24 weeks during the double-blinded treatment period. However, on scheduled visits participants will have the IP administered on site after the blood sample collection. The drug dose during the treatment phase will be checked and verified with study medication compliance by using drug accountability form.

[figure not shown]
7.7 Schedule of Assessment

Schedule of Assessment table is provided in [Appendix 1](#)

7.8 Study Flow Chart

The study plan is as follow:

Document Title:	Statistical Analysis Plan		
Version Number:	Final 1.0	Date:	18Oct2024
Protocol Number:	SARO.17.009	Sponsor Name:	Zydus Therapeutics INC

Document Title:	Statistical Analysis Plan		
Version Number:	Final 1.0	Date:	18Oct2024
Protocol Number:	SARO.17.009	Sponsor Name:	Zydus Therapeutics INC

8 General Statistical Considerations

8.1 Descriptive Statistics

The following descriptive statistics will be calculated for continuous data as well as for categorical data:

The summary statistics will be displayed with the following digits:

Description	Characteristic	Number of Decimal Places
Number of non-missing participants/observations	n	0
Number of events	E	0
Count corresponding to the number of participants for a group	N	0
Percentage [#]	%	1 decimal
Number of missing observations*	Missing	0
Mean	Mean	As in source + 1
Adjusted Least Square Mean	LS Mean	As in source +1
Standard Deviation	SD	As in source + 2
Standard Error	SE	As in source + 2
Minimum	Min	As in source
Median	Median	As in source + 1
Maximum	Max	As in source
Probability value	p-value	4 decimals
Confidence Interval	CI	2 decimals
Change From Baseline values	CFB	As in source
Percent Change from Baseline	PCB	2 decimals

*: If no observation is missing then “nmiss” row will not be printed.

#: Number of decimal places can be more than one, if necessary. All table percentages should be rounded to one decimal place if not stated otherwise.

Data will be summarized by the treatment groups (i.e. Saroglitazar Magnesium 4 mg or Placebo) wherever appropriate. The total number of participants in the treatment groups (N) under the stated population will be displayed in the header of summary tables as required.

Data will be summarized using descriptive statistics for continuous variables. Unless otherwise stated, descriptive statistics will include total number of participants with non-missing value of a variable/parameter (n), mean (Mean), Standard Deviation (SD), minimum (Min), median (Median), and maximum (Max).

In case of n=1, (where ‘n’ indicates the number of evaluable participants at the particular time point) then “SD” will be presented as ‘NE’ i.e. ‘Not Evaluable’.

In case of n<1, (where ‘n’ indicates the number of evaluable participants at the particular time point) then “Mean, SD, Median, Minimum, Maximum” will be presented as ‘NE’ i.e. ‘Not Evaluable’.

Document Title:	Statistical Analysis Plan		
Version Number:	Final 1.0	Date:	18Oct2024
Protocol Number:	SARO.17.009	Sponsor Name:	Zydus Therapeutics INC

For categorical variables, data will be summarized using numbers of frequency count and percentages. The number [n] indicates the actual number of participants with a particular value of a variable or event, which should always be less than or equal to the total number of participants in the respective treatment group [N], unless participant is counted under multiple categories. The number and percentage of participants with missing values for a variable/category/event will also be presented for the resulting visits under the “Missing” category.

All data will be presented in the participant data listings. If either table or listing does not include any observation, then the following placeholder will be used: “No Participant Meets the Reporting Criteria”.

8.2 Analysis Populations

Participant evaluability and their impact on analysis populations will be determined prior to locking the database.

Analysis Population	Definition
Safety (SAF)	The Safety (SAF) analysis population will consist of all participants who: - Were Randomized, - Had administered at least one dose of investigational product.
Modified Intention to Treat (mITT)	Modified Intention to Treat analysis population will consist of all participants who: - Were randomized, - Had administered at least one dose of investigational product - Have at least 1 post-baseline efficacy data of primary outcome.
Per Protocol (PP)	The Per Protocol (PP) analysis population will consist of all participants who: - Were in mITT analysis population, - Completed the treatment phase (i.e., Had both baseline and end-of-treatment primary efficacy outcome & has taken $\geq 80\%$ and $\leq 120\%$ of the study drug) - Have no protocol deviations that could affect primary efficacy outcome.

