Visit 2 (Day -14 to -7): Liver function tests (AST, ALT, ALP, GGT, total protein, albumin, total bilirubin (with conjugated bilirubin) will be re-measured approximately 2 weeks from Day - 28 to determine eligibility.

Alanine transaminase ≥ 38 U/L at Visit 1. Visit 2 ALT must not increase $>30\%$ from Visit 1.

Randomization and Treatment Phase

Visit 3 to Visit 8: The randomization and treatment phase will include 6 outpatient visits (Visit 3 to Visit 8) over a period of 24 weeks including the randomization visit. All the eligible subjects will be randomly assigned into either of the two treatments arms: Saroglitazar Magnesium 4 mg Tablets and matching placebo tablets in a 1:1 ratio. Efficacy assessments will be conducted at 12 (hormonal profile, lipid and lipoprotein profiles, ovarian function and liver enzymes/LFTs) and 24 weeks visits (liver fat content by MRI-PDFF, hormonal profile, lipid and lipoprotein profiles, MRI-derived total liver fat index and total liver volume, homeostasis model assessment [insulin resistance (HOMA-IR)], liver stiffness by transient elastography/FibroScan®, controlled attenuation parameter, ovarian function and liver enzymes/LFTs). In addition, subjects will be monitored during the study and at every visit for development of any adverse events including drug induced liver injury. In addition to physical examination, laboratory data and ECGs done during the study period will be monitored to detect any treatment emergent adverse events.

Visit 3 (Week 1, Day 1): Patients will be randomly assigned to receive Saroglitazar Magnesium 4 mg Tablets or placebo orally once-daily, starting on Day 1 of a 24-week outpatient treatment period.

Visits 4, 5, 6, 7 and 8: Patients will visit the study site at Week 2 (Visit 4), Week 8 (Visit 5) Week 12 (Visit 6), Week 16 (Visit 7) and Week 24 (Visit 8) for clinical assessment, dispensation and reconciliation of study drug, measurements of efficacy endpoints and assessment of AEs.

Detailed efficacy and safety assessments are provided in Table 1 (Time and Events Schedule).

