8.4.1.2 Modified Intent-to-treat population (mITT)

The mITT population will consist of all randomized patients who received at least 1 dose of the study drug and have at least 1 post-baseline efficacy data.

Last observation carried forward method will be used as an imputation method for post-baseline missing values for mITT analysis.

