8.5 HANDLING OF MISSING DATA

Clarifications, wherever possible, will be obtained from the respective Investigator for any missing data or for any illegible entry, unused or unauthenticated data and this will be recorded in the data handling report before the final database lock.

Subjects who are discontinued from the study will be excluded from PP population. Any randomized subject who discontinued the study for any reason but have at least 1 post-baseline efficacy data will be included in the mITT population. Last Observation Carried Forward method will be used as an imputation method for the efficacy variables for mITT population.

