7.2 Study Methodology

Pre-Screening:

An informed consent will be obtained from the potential participants before any pre-screening evaluations. The evaluation of the ALT levels during the pre-screening will be done at the local laboratory, whereas the laboratory evaluations during the screening and the treatment phase will be done at the central laboratory.

Screening Phase:

The screening phase will consist of 28 days. Unless otherwise specified, screening procedures may be completed at any time during the screening phase. Before each participant is enrolled to the study, informed consent will be obtained from the participant (or her legally authorized representative) according to the regulatory and legal requirements of the participating country. Participant eligibility criteria for participation in the study will be assessed. Participants will undergo a serum pregnancy test. During this phase participant will be seen by the investigator or designated study personnel and an AUDIT questionnaire will be administered.

Randomization and Treatment Phase:

The randomization and treatment phase will include 6 outpatient visits (Visit 3 to Visit 8) over a period of 24 weeks including the randomization visit. All the eligible participants will be randomly assigned into either of the two treatment arms: Saroglitazar Magnesium 4 mg tablets and matching placebo tablets in a 1:1 ratio. Efficacy assessments will be conducted at Visit 6 Week 12 and Visit 8 Week 24 visits. In addition,

Document Title:	Statistical Analysis Plan		
Version Number:	Final 1.0	Date:	18Oct2024
Protocol Number:	SARO.17.009	Sponsor Name:	Zydus Therapeutics INC

participants will be monitored during the study and at every visit for development of any adverse events including drug induced liver injury. In addition to physical examination, laboratory data and ECGs done during the study period will be monitored to detect any treatment emergent adverse events.

Safety Follow-up Visit:

A final post-treatment visit will occur 6 weeks (± 3 days) [i.e. Visit 9 Week 30] after the end-of-treatment visit (i.e. Visit 8 Week 24) for safety monitoring. A telephonic follow-up visit will be performed to assess any AE or SAE after the end-of-treatment visit for safety monitoring. As far as possible, all assessments scheduled for end-of-treatment must be performed on all participants who receive the study drug but do not complete the study according to protocol.

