8.4 Handling of Dropouts and Missing data

Clarifications, wherever possible, will be obtained from the respective Investigator or data management team for any missing data or for any illegible entry, unused or unauthenticated data and this will be recorded in the data handling report (If required) before the final database lock.

Dropouts and missing values, considering missing values as missing at random (MAR) will be imputed by using multiple imputation method for primary efficacy variable, for mITT population only, and will be considered as supportive to the analysis.

Dropouts and missing values will not be imputed for safety and secondary endpoints.

Imputed data should be flagged and properly footnoted as “imputed”. Title should indicate that imputed data is used for summary.

Adverse events with unknown end date/time will be counted as an ongoing AEs, if ongoing is ticked on the CRF. Medications with unknown end date/time will be considered as concomitant. Adverse events and medications with partially missing start or end dates will be considered ongoing and concomitant respectively unless the non-missing portion of the dates definitively proves otherwise.

Document Title:	Statistical Analysis Plan		
Version Number:	Final 1.0	Date:	18Oct2024
Protocol Number:	SARO.17.009	Sponsor Name:	Zydus Therapeutics INC

Partial dates for Adverse events and medications will be imputed as follows for derivation of treatment emergent and Prior/Concomitant flags respectively:

- Missing day in start date of a time period is imputed by the first day of the month.
- Missing day in end date of a time period is imputed by the last day of the month.
- Missing month in start date of a time period is imputed by January of the year.
- Missing month in end date of a time period is imputed by December of the year.
- Missing year is not imputed.
- After above imputation if start or end date is after Participant's end of study date then start or end date is set to Participant's end of study date.

If required, time will be imputed in the following way:

Times should be printed in the format "HH:MM". "HH" represents the 2-digit hour portion of the time. "MM" represents the 2-digit minute portion of the time. Both hour and minute portions of time are zero padded integer values. Missing time portions should be represented on Participant listings as dashes ("10:--" and "--:--").

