9.7.1.2 Estimand

The attributes for the primary estimand related to the first primary endpoint are described below:

1. Treatment: The study compares the efficacy of the Investigational Product (i.e., Saroglitazar Magnesium 4mg) versus the Placebo as randomized in 1:1 ratio.
2. Population: The target population is female participants of PCOS with NAFLD, 18 to 45 years of age. Primarily, analysis will be based on the PP population.
3. Variable: The primary endpoint is the “Change in hepatic fat content from baseline to Week 24” measured by MRI-PDFF.
4. Intercurrent Events:

Document Title:	Statistical Analysis Plan		
Version Number:	Final 1.0	Date:	18Oct2024
Protocol Number:	SARO.17.009	Sponsor Name:	Zydus Therapeutics INC

- Missing Data: Participants may discontinue the study treatment before completing the Visit 8 (Week 24) period, might miss the Week 24 MRI-PDFF measurement, will be considered as missing. The missing data values may be imputed for primary endpoint analysis to consider the analysis treatment effect assuming all participants completed treatment as planned.
- Rescue/Concomitant medication: Participants might require additional treatments (rescue medication or concomitant medications) during the treatment period. The effect of the study treatment will be evaluated regardless of the rescue or concomitant medication.
- Change in ALT inclusion criteria: Participants recruited before the amendment may not fulfill the ALT inclusion criteria due to absence of inclusion criterion. A selection bias will be handled by conducting sensitive analysis, for analyzing subgroup treatment difference (within stratum) based on the ALT score, which will lead to assess whether the change in inclusion criteria has influenced the treatment effect. OR adjustment of the covariates for ALT levels can be performed.

5. Population Level Summary:

The primary efficacy endpoint, the change from baseline in hepatic fat content at Visit 8 (Week 24) will be analyzed using an analysis of covariance (ANCOVA) model. The effectiveness of the investigational product (Saroglitzazar magnesium 4 mg) will be achieved using the lower bound of the 95% confidence interval of the LS Mean difference between the treatment groups.

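### The SAP's mITT set excludes any woman without a post-baseline MRI-PDFF, so dropouts without a scan are removed before the multiple imputation planned for them, and SAP Section 10 does not list the change

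*SAP*

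**What the plan says.** **Who is in mITT.** Protocol 8.4.1.2 takes randomised patients who "received at least 1 dose of the study drug and have at least 1 post-baseline efficacy data". Protocol 8.5 applies this to leavers: any randomised subject "who discontinued the study for any reason but have at least 1 post-baseline efficacy data will be included in the mITT population". SAP 8.2 keeps the randomisation and dosing conditions but changes the third to "Have at least 1 post-baseline efficacy data of primary outcome".

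**When the primary outcome is measured.** Baseline MRI-PDFF is taken in screening. In Protocol 7.2, MRI-PDFF is absent from the Week 12 list and first appears at the "24 weeks visits (liver fat content by MRI-PDFF, hormonal profile". Protocol 6.1.2 likewise gives the MRI-derived secondary measures at Week 24 only. For women who stop early, SAP 7.2 asks that, where feasible, "all assessments scheduled for end-of-treatment must be performed on all participants who receive the study drug but do not complete the study".

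**What is imputed.** SAP 8.4 says dropouts and missing values "will be imputed by using multiple imputation method for primary efficacy variable, for mITT population only", as a supportive analysis. The estimand in SAP 9.7.1.2 names the woman who stops treatment and "might miss the Week 24 MRI-PDFF measurement, will be considered as missing", and adds: "The missing data values may be imputed for primary endpoint analysis". SAP 9.7.1.4 describes imputation as serving the primary analysis and names no predictors. SAP 9.7.1.5 runs per-protocol without imputation and mITT with it.

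**What is declared.** SAP Section 10 has five rows: terminology, missing-value imputation, subgroups, estimand and statistical significance. The move from LOCF to multiple imputation is there. The new mITT condition is not, although SAP Section 5 says changes from the protocol's analysis are detailed in the SAP.

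**The concern.** Imputation can act only on a woman who is in the analysis set with her value missing. Here the condition for entering the set is having the value. If the one post-baseline scan is at Week 24, the SAP's mITT set has no missing primary value, and the imputed mITT analysis is an ANCOVA on observed scans.

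This analysis is the only one in the plan meant to address dropout. Per-protocol is a subset of mITT and also requires both scans. Agreement between the two would be read as robustness to dropout, although no unscanned dropout is in either. Secondary efficacy analyses use the same two sets, so these women's Week 12 values also leave the supportive mITT ANCOVAs.

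**Working it through.** **1. The definitions, followed through for a woman who stops after Week 12 with no later scan**

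| Step | Protocol | SAP |
|---|---|---|
| Has a post-baseline efficacy value (e.g. Week 12 ALT) | yes | yes |
| Has a post-baseline primary-outcome value | not required | no |
| In mITT | yes | no |
| Primary value filled in | by LOCF | not imputed, because imputation is for mITT only |

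If a dropout does have an early scan, she enters mITT. If that scan counts as Week 24, nothing is imputed. If it does not, imputation acts on these women only. The visible text does not say which. Neither reading brings in the unscanned woman.

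**2. How many women**

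Inputs: recruitment closed at 60 and 20% dropout assumed (SAP 8.5).

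- Dropouts: 60 × 0.20 = 12.
- Lost = 12 × (1 − share scanned early): 12 if none, 12 × 0.75 = 9 if a quarter, 12 × 0.50 = 6 if half.
- SAP mITT size: 48, 51 or 54 of 60.
- Range with no early scans: 10% dropout loses 6 (mITT 54); 30% loses 18 (mITT 42).

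**3. What it could do to the estimate (illustration; inputs assumed)**

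The plan gives no usable SD. Its stated 0.6 with a 4-point difference does not lead to 37 per arm. A 4-point difference with 37 per arm and 80% power implies an SD of 6.06, so SD 6 is used. Other assumptions: 30 per arm, 6 missing per arm, true hypothetical difference −4, and a Week 12 marker with correlation r to the Week 24 change. Each cell is 1,500 simulated trials; imputation is by arm (m = 20) with Rubin's rules, then ANCOVA on baseline. Missingness is at random given the marker by construction.

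| Who goes missing | r | Scanned only | MI, baseline only | MI, baseline + marker |
|---|---|---|---|---|
| By baseline PDFF | 0.5 | −3.99 | −3.98 | −3.98 |
| Poor marker, active arm | 0.3 | −4.43 | −4.43 | −3.98 |
| Poor marker, active arm | 0.5 | −4.70 | −4.70 | −3.99 |
| Poor marker, active arm | 0.7 | −5.01 | −5.01 | −3.99 |
| Poor marker, placebo arm | 0.3 | −3.62 | −3.63 | −4.07 |
| Poor marker, placebo arm | 0.5 | −3.29 | −3.29 | −4.03 |
| Poor marker, placebo arm | 0.7 | −2.99 | −2.99 | −4.00 |

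Hand check: losing the worst 20% on a score correlated ρ with the change shifts the remaining mean by ρ × SD × φ(0.84)/0.8 = ρ × 6 × 0.35. If the score is the marker plus unrelated noise of equal variance, ρ = 0.5 × 0.707, the shift is 0.74 and the estimate is about −4.74 (table: −4.70). If the marker alone decides, the shift is 0.5 × 6 × 0.35 = 1.05, giving about −5.05.

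The table shows three things. If missingness depends only on arm and baseline, nothing is lost. If it depends on the Week 12 course, the scanned-only estimate moves, in a direction set by which arm loses poor responders. Imputation from baseline alone reproduces the scanned-only result, so wider mITT entry helps only if the imputation model uses post-baseline information.

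**The case against.** - **The counts may overstate the effect of the wording.** A woman who leaves before any efficacy value is outside mITT under both definitions. If half of the dropouts leave before Week 12 with no such value, 12, 9 and 6 become about 6, 4–5 and 3. This stands as a caution. Its force is limited: weight is a secondary efficacy variable and part of the physical examination, held at Weeks 2 and 8 as well (SAP 6.3 and 9.8.5). The protocol's wording would keep most early leavers if those weights count as efficacy data.
- **The illustration is near a best case for the fix.** It assumes no early scans and a Week 12 marker for every missing woman. With half the dropouts scanned early and half of the rest lacking Week 12 data, scanned-only averages −4.32 and marker-based filling-in −4.16. The bias falls to about 0.3 and the fix removes about half of it. The definitional point does not depend on these figures.
- **Week 24 as the only scan is inferred.** The schedule tables are not readable, and the Week 12 list in Protocol 7.2 omits some items due then, such as weight and HOMA. Protocol 6.1.2 makes the inference likely: it gives the MRI-derived measures at Week 24 only.
- **The conflict over imputation is partly loose wording.** Per-protocol requires both scans, so there is nothing to impute in it. That is fair, but the four sections still need to say the same thing.
- **Week 12 laboratory values are not lost altogether.** They remain in the safety summaries (SAP 9.8.2). The loss is from the efficacy ANCOVAs.
- **Only a supportive analysis is affected.** That is correct and limits the severity.

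**Conclusion.** The concern holds. As written, the SAP's mITT condition removes the unscanned dropout from the only set in which she could be imputed, so the planned imputation has nothing, or almost nothing, to act on. It also departs from the protocol's definition without being listed in Section 10.

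At the planned 20% dropout, 6 to 12 of 60 women are lost to every efficacy analysis if between half and none of the dropouts have an early scan. Restoring the protocol wording recovers those with some post-baseline efficacy value. Bias is possible, not demonstrated: scanned-only ANCOVA is unbiased for the hypothetical effect if missingness depends only on arm and baseline PDFF. Otherwise the direction cannot be predicted. The conclusion rests on the visit text, since the schedule tables cannot be read. The primary per-protocol analysis is not changed by it. This should be fixed, but it does not affect the primary test.

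**What to change.** 1. SAP 8.2: delete the last three words of the mITT condition, restoring the protocol's definition. If a wider set is preferred (randomised, dosed, with a baseline PDFF), list it in Section 10.
2. SAP 9.7.1.4: specify imputation of Week 24 PDFF by arm, by regression on baseline PDFF and named Week 12 variables already collected, such as ALT and weight. SAP 9.7.1.4 already permits a regression method; naming the predictors matters because baseline alone adds nothing.
3. State whether a scan taken at early termination counts as the Week 24 value.
4. Make SAP 8.4, 9.7.1.2, 9.7.1.4 and 9.7.1.5 agree: per-protocol is primary and not imputed; imputation is for the supportive mITT analysis only. Stop labelling these two as sensitivity analyses, since they are the primary and supportive analyses again.

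Per-protocol can remain primary as prespecified. The cost is SAP wording, one imputation model and modest programming, with no new data. The supportive estimate may move either way, and its interval may widen slightly: in the illustration (r = 0.5, active-arm case) the mean standard error rises from 1.72 to 1.79, and 1.79/1.72 = 1.04. Women who leave before Week 12 have no Week 12 values, so those predictors cannot help for them. If the database is already locked, the change can be reported with its reason in the study report, as SAP Section 5 provides.
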